### 3.4.3 Secondary Endpoints

#### Safety

For the main safety parameters, 95% CIs of point estimates will be calculated using exact binomial method (Clopper-Pearson method) for single proportions and using the normal approximation for quantitative data.

All analyses will be descriptive; no hypotheses will be tested.

The number of participants with documented safety will be used as denominator of the frequencies:

- For solicited reactions, the denominator will be the total number of participants who have non-missing data for the endpoint considered.
- For unsolicited AEs, the denominator will be the total number of participants who were vaccinated with the dose analyzed.

In terms of contents, solicited reactions will be presented by time to onset, maximum severity, number of days of occurrence and action taken; unsolicited AEs will be presented by causal relationship, time of onset, maximum severity, and duration; SAEs will be presented by causal relationship, seriousness, and outcome.

Subgroup analysis will also be performed; in particular, the main safety endpoints will be summarized according to age subgroups, sex, and race, as appropriate according to number of participants in the respective subgroups.

### **3.4.4 Handling of Missing Data and Outliers**

#### **3.4.4.1 Immunogenicity**

No imputation of missing values and no search for outliers will be performed. LLOQ and ULOQ management will be performed as described in [Section 4.2.1.1](#).

#### **3.4.4.2 Safety**

No replacement will be done for Safety Missing Data and Outliers.

##### **3.4.4.2.1 Immediate**

For unsolicited systemic AEs, a missing response to the “Immediate” field is assumed to have occurred after the 30-minute surveillance period and will not be imputed.

##### **3.4.4.2.2 Causal Relationship**

By convention, all events reported at the injection site (either solicited or unsolicited) will be considered as related to the administered product and then referred to as reactions. In a same way, all solicited systemic events pre-listed in the eCRF are also considered as related to vaccination and will be considered as reactions.

- For unsolicited systemic AE, missing relationship will be considered as related to study vaccine at the time of analysis
- The missing relationship to study procedures for SAEs will not be imputed

##### **3.4.4.2.3 Intensity**

For solicited reactions, missing intensities will be handled as described in [Section 4.2.2.1.2](#). For unsolicited AEs, missing intensities will remain missing and will not be imputed.

##### **3.4.4.2.4 Start Date and End Date**

Missing or partially missing start dates or end dates for unsolicited AEs (including SAEs) will remain missing and not be imputed. If the start date is missing or partially missing, the time of onset will be set to missing. If either the start date or end date is missing or partially missing, the duration will be considered missing.

Missing or partially missing end dates for ongoing solicited AEs will remain missing and not be imputed.

##### **3.4.4.2.5 Action Taken**

Missing actions taken will remain missing and not be imputed.

### 3.5 Interim Analysis

The blind will be broken at the participant level after collecting all immunogenicity and safety data up to 21 days after last vaccination, data are cleaned, and database is locked. The study participants and the laboratory personnel who analyze the blood samples will remain blinded throughout the study. The study team will strive not to communicate the study unblinded data to the sites until the interim CSR sign-off, to minimize the bias in collecting the follow-up safety data.

The main analysis of immunogenicity (HIH and SN measurement methods) data and safety will include all data up to 21 days after the last vaccination. The results of this analysis will help in selecting the dose formulation for further clinical development. The results of this main analysis may be reported in an interim clinical study report (CSR).

HIH and/or SN results will be evaluated, discussed, and used in selecting the best Panblok formulation with the most suitable immunogenicity response and safety for further clinical development.

A final database lock will occur after all data, including up to the 12-month follow-up period, are collected. A final CSR would include the analysis of the safety and immunogenicity data at 6- and 12-month after the last vaccination to assess the persistence of the antibody levels.

No hypothesis will be tested, thus adjustment for multiplicity is not necessary.

Unblinded early looks at the safety data may take place to assess safety.

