- by the Global Pharmacovigilance (GPV) Department through an internal system for reporting to Health Authorities in the case of an unexpected SAE considered causally related, as described in International Council for Harmonisation (ICH) E2A. In this case, the code will be broken only for the participant(s) in question. The information resulting from code-breaking (ie, the participant's study intervention or group assignment) will not be communicated to either the investigator or the immediate team working on the study, except for the GPV representative.

At the time of the interim analysis (see [Section 9.5](#)), study unblinding will take place to inform selection of the dose formulation for Phase III clinical development. The unblinding code data will be maintained with the Sponsor until the end of the study. The study team will strive not to communicate the study unblinding data to sites in order to minimize bias in collecting the follow-up safety data. The study participants and the laboratory personnel who analyze the blood samples for the study will remain blinded throughout the study.

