## 8 Study Assessments and Procedures

- Study procedures and their timing are summarized in the SoA. Protocol waivers or exemptions are not allowed.
- Immediate safety concerns should be discussed with the Sponsor immediately upon occurrence or awareness to determine if the participant should continue or discontinue study intervention.
- Adherence to the study design requirements, including those specified in the SoA, is essential and required for study conduct.
- All screening evaluations must be completed and reviewed to confirm that potential participants meet all eligibility criteria. The investigator will maintain a screening log to

record details of all participants screened and to confirm eligibility or record reasons for screening failure, as applicable.

- Safety / laboratory results that could unblind the study will not be reported to sites or other blinded personnel until the study has been unblinded.

Urine (as applicable) and blood samples will be collected as described in the SoA table ([Section 1.2](#)).

The maximum amount of blood collected from each participant over the duration of the study, including any extra assessments that may be required, is not planned to exceed 240 mL. Repeat or unscheduled samples may be taken for safety reasons or for technical issues with the samples.

Guidance and information for the sample collection, preparation, storage, and shipment will be provided to the study personnel.

For a regional or national emergency declared by a governmental agency, contingency measures are included in [Appendix 10.5: Contingency Measures for a regional or national emergency](#) that is declared by a governmental agency.

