#### **8.3.3 Follow-up of AEs and SAEs**

After the initial AE/SAE report, the investigator is required to proactively follow each participant at subsequent visits/contacts, unless a participant refuses further contact. All AEs that are

considered by the investigator as serious, or related to the study intervention administered, or that led to study or vaccination discontinuation, or AESIs (as defined in [Section 8.3.6](#)), will be followed during the conduct of the study until resolution, stabilization, or the participant is lost to follow-up (as defined in [Section 7.3](#)). For related SAEs ongoing at last study visit, such follow-up may need to continue after the end of the study.

Further information on follow-up procedures is provided in [Appendix 10.3](#).

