### 9.4.1 General Considerations

The statistical analysis will be conducted as follows:

- The study will be unblinded after all immunogenicity and safety data are collected for the follow-up period of 3 weeks after D22 (ie, 21 days after the last vaccination) (see [Section 6.3.2](#) and [Section 9.5](#)).
- The final database lock will occur after the 12-month follow-up.

No adjustment for multiplicity regarding multiple comparisons between study doses is planned in this study. Details will be provided in the SAP.

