### **9.5 Interim Analyses**

The blind will be broken at the participant level after collecting all immunogenicity and safety data up to 21 days after last vaccination, data are cleaned, and database is locked. The study participants and the laboratory personnel who analyze the blood samples will remain blinded throughout the study. The study team will strive not to communicate the study unblinded data to the sites in order to minimize the bias in collecting the follow-up safety data.

The main analysis of immunogenicity (HIH and SN measurement methods) data and safety will include all data up to 21 days after the last vaccination. The results of this analysis will help in selecting the dose formulation for further clinical development. The results of this main analysis may be reported in an interim clinical study report (CSR).

A final database lock will occur after all data, including up to the 12-month follow-up period, are collected. A final CSR would include the analysis of the safety and immunogenicity data at 6- and 12-month after the last vaccination to assess the persistence of the antibody levels.

No statistical adjustment is necessary because no hypothesis will be tested. Unblinded early looks at the safety data may take place to assess safety.

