- There may be situations in which an SAE has occurred and the investigator has minimal information to include in the initial report to the Sponsor. However, it is very important that the investigator always makes an assessment of causal relationship for every event before the initial transmission of the SAE data to the Sponsor.
- The investigator may change his/her opinion of causal relationship in light of follow-up information and send an SAE follow-up report with the updated causal relationship assessment.
- The causal relationship assessment is one of the criteria used when determining regulatory reporting requirements.

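### SAP 3.5 stops the commitment to keep unblinded data from sites at interim CSR sign-off; protocol 6.3.2 and 9.5 set no such end point, and sign-off can fall during the 12-month safety follow-up.

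*SAP*

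**What the plan says.** Both documents break the blind at participant level once the data to 21 days after dose 2 are collected, cleaned and locked. They differ on how long sites are then shielded.

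- SAP 3.5: "The study team will strive not to communicate the study unblinded data to the sites until the interim CSR sign-off". The stated reason is to limit bias in follow-up safety data.
- Protocol 9.5: "The study team will strive not to communicate the study unblinded data to the sites in order to minimize the bias". The reason is the same and no end point is given.
- Protocol 6.3.2: the team will "strive not to communicate the study unblinding data to sites in order to minimize bias in collecting the follow-up safety data". Again there is no end point.
- Protocol 6.3.2 also says: "The unblinding code data will be maintained with the Sponsor until the end of the study". Section 4.4 defines the end of the study as the final visit of the final participant.

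The general rule in protocol 6.3.2 is that investigators and staff who assess safety do not know which vaccine was given. SAP Table 1.1 also lists the investigator as blinded. SAP section 5, on changes to planned analyses, is marked not applicable.

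**The concern.** The SAP end point does not serve its own stated purpose. The aim is to protect safety data collected after D43, yet the commitment stops at an event tied to the D43 report rather than to the end of that collection. Under protocol 8.3.1, MAAEs and AESIs are collected throughout the study and SAEs until 12 months after the last vaccination. Investigators assess whether unsolicited systemic events are related to vaccine, and Appendix 10.3.3 adds: "The investigator may change his/her opinion of causal relationship in light of follow-up information".

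If sites held participant-level assignments before these data were final, recording or causality judgments could differ between the adjuvanted and unadjuvanted groups. For SAEs and non-serious AESIs the Sponsor also assesses causality, but the documents do not say whether its assessors remain blinded after D43. Protocol 9.5 and SAP 3.5 name participants and laboratory personnel as blinded throughout; for sites after D43 those sections offer only the commitment at issue.

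**Working it through.** **1. Text comparison.**

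| Place | Commitment | End point |
|---|---|---|
| Protocol 6.3.2 | strive not to tell sites | none stated |
| Protocol 9.5 | strive not to tell sites | none stated |
| Protocol 6.3.2, code custody | Sponsor holds the code | end of study |
| SAP 3.5 | strive not to tell sites | interim CSR sign-off |

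The SAP is the only one of these with an end point that can precede the last visit.

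**2. Follow-up remaining after D43.** Inputs are from the schedule of activities: V02 at D22; V03 at D43 (+7 days), set from V02; V05 at D387 (+14 days), set from V02. The schedule agrees with itself: 43 − 22 = 21 days and 387 − 22 = 365 days.

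- Nominal gap, V03 to V05: 387 − 43 = 344 days (344 / 30.4375 = 11.3 months).
- Shortest (V03 late, V05 on time): 365 − 28 = 337 days.
- Longest (V03 on time, V05 late): 379 − 21 = 358 days.

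**3. Follow-up remaining at sign-off.** Neither document dates the sign-off, so the times below are assumptions. With sign-off s days after the last participant's D43 visit, that participant has 344 − s days left (range 337 − s to 358 − s, not below 0).

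| Assumed sign-off | s | Days left, nominal (range) | Share of 344 |
|---|---|---|---|
| 3 months | 91 | 253 (246–267) | 253/344 = 74% |
| 6 months | 183 | 161 (154–175) | 161/344 = 47% |
| 9 months | 274 | 70 (63–84) | 70/344 = 20% |
| 12 months | 365 | 0 (0) | 0% |

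These are upper bounds for the study as a whole. They describe the last participant; those enrolled earlier have less follow-up left on the same date. The documents give no enrolment duration, so study-wide exposure cannot be calculated.

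**4. Size of the bias.** The documents provide nothing from which to estimate it.

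**The case against.** The strongest reply is that little practical risk remains. The wording is only to strive; its lapse does not say that anything will be sent. Protocol 6.3.2 still blinds safety assessors and keeps the code with the Sponsor to the end of the study, and SAP 3.4 says the SAP is to be used together with the protocol. Group-level results alone would not reveal an individual's vaccine. Safety is secondary and descriptive. All of this stands and limits the severity. It does not remove the difference in wording.

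A reader might be tempted by three stronger readings that the documents do not support.

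- *That the SAP end point is undefined if no interim CSR is written.* The report is indeed optional. But when a restriction runs until an event that never occurs, the natural reading is that it continues, which matches the protocol.
- *That protocol section 8 releases sites even earlier.* It says results that could unblind "will not be reported to sites or other blinded personnel until the study has been unblinded", and section 9.4.1 says: "The study will be unblinded after all immunogenicity and safety data are collected for the follow-up period of 3 weeks after D22". But section 8 concerns safety and laboratory results, not treatment codes. Safety laboratory tests are not applicable (8.2.4), and pregnancy testing is the only protocol-required safety test (Table 10.1). Section 8 also covers other blinded personnel, yet laboratory staff remain blinded throughout, so a literal release at D43 would contradict 6.3.2 and 9.5. Those specific sections govern.
- *That the protocol must be amended.* Its commitment is already the stronger one. Adding a final-lock end point to 6.3.2 would leave that section with two different end points, since code custody runs to the end of the study.

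**Conclusion.** The point holds as a minor SAP–protocol inconsistency. SAP 3.5 adds an end point that protocol 6.3.2 and 9.5 lack, does not declare it as a change, and so allows the commitment to lapse while follow-up safety data are still being collected. Only the opportunity can be sized: a nominal 344 days (337 to 358) per participant between D43 and D387. How much of that remains at sign-off depends on an assumed date and is at most the last participant's figure. It would be nil if sign-off came about 11 to 12 months or more after the last D43 visit.

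It should not be read as a planned or authorised unblinding of sites, nor as evidence of bias, which may be zero. The D43 immunogenicity and safety analysis used for dose selection is unaffected because those data are locked before the blind is broken.

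**What to change.** Change SAP 3.5 only. Either delete the clause that ends the commitment at interim CSR sign-off, which restores agreement with protocol 6.3.2 and 9.5, or replace it with an end at final database lock.

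Final lock is a sensible choice if an explicit end point is wanted. It follows collection of the 12-month data and allows for late revisions of causality. It does not cover every case: protocol 8.3.3 notes "For related SAEs ongoing at last study visit, such follow-up may need to continue after the end of the study", with no limit tied to lock.

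The protocol, including section 8, can stay as it is. This avoids the amendment approvals described in Appendix 10.1.1. Emergency code-breaking under 6.3.2 is untouched.

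The cost is one clause, with no change to data, sample size or analysis. Sites would receive unblinded interim results later. One practical detail needs settling: Appendix 10.1.7 has the clinical study report signed by the coordinating investigator, or by another identified investigator, without distinguishing interim from final reports. If that applies to the interim CSR, the signatory needs a stated exception or a version without participant-level assignments.

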#### *Medically Attended Adverse Events (MAAEs)*

MAAEs will be collected throughout the study.

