### ***Medically Attended Adverse Events***

MAAE safety summaries will be reported for within 21 days after each vaccination, from D01 to D42, from D43 to D202, from D203 to D387, and overall study.

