#### 10.1.5 Committees Structure

Participant safety will be continuously monitored by the Sponsor's internal safety review committee which includes safety signal detection at any time during the study. The Sponsor's internal safety review committee, led by the PV representative and the RMO and designee(s), will be responsible for the blinded review, assessment, and evaluation of safety data generated from this study up to the D43 data unblinding for the main analysis. This committee is empowered to recommend a pause in recruitment and/or further vaccination while it investigates any potential signal or concern.

This study will not include an early safety data review.

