**Table 1.2: Schedule of activities**

**Phase I/II Study, 5 Visits, 2 Vaccinations, 5 Blood Samples, 13 Months' Duration Per Participant**

Visit/Contact	Collection of information in the CRF	Visit 1	Visit 2	Visit 3	Visit 4	Visit 5
Study timelines (days)		D01	21 days post V01 (D22)	21 days post V02 (D43)	6 months post V02 (D202)	12 months post V02 (D387)
Time windows (days)			[+7 D]	[+7 D]	[+14 D]	[+14 D]
Visit procedures:						
Informed consent	X	X				
Inclusion/exclusion criteria	X	X				
Collection of demographic data	X	X				
Urine pregnancy test (if applicable)		X	X			
Collection of Medical history	X Significant Medical History	X				
Physical examination		X	X			
Temporary and definitive contraindications	X		X			
Pre-vaccination temperature		X	X			
Randomization	X	X				
Allocation of participant number	X	X				
Dose assignment by IRT		X	X			
Blood sampling (BL) [40 mL/visit]	X	BL0001 Pre-vac	BL0002 Pre-vac	BL0003	BL0004	BL0005
Vaccination (vac)	X	X	X			

Visit/Contact	Collection of information in the CRF	Visit 1	Visit 2	Visit 3	Visit 4	Visit 5
Visit/Contact	Collection of information in the CRF	Visit 1	Visit 2	Visit 3	Visit 4	Visit 5
Diary card/eDiary provided†		DC1/eDC	DC2	DC3	DC4	
Diary card/eDiary reviewed			DC1/eDC	DC2/eDC	DC3/eDC	DC4/eDC
Diary card collected‡			DC1	DC2	DC3	DC4
Collection of solicited injection site and systemic reactions	X	X	X	X		
Collection of unsolicited adverse events (AEs)	X	X	X	X		
Collection of concomitant medications	X Reportable concomitant medication	X	X	X		
Collection of serious adverse events (SAEs), including AESIs	X	To be reported at any time during the study				
Collection of pregnancies	X	To be reported at any time during the study				
End of Study Intervention Phase§	X			X		
End of study**	X					X

AESI: adverse event of special interest; CRF: case report form; D: day; DC: diary card; IRT: interactive response technology; V: visit

[figure not shown]
† The investigator or an authorized designee will remind the participants to bring back the DC at the next visit and will answer any questions.

‡ The investigator or an authorized designee will interview the participants to collect the information recorded in the DC and will attempt to clarify anything that is incomplete or unclear.

§ In case of participant discontinuation at a visit, the entire visit will be completed.

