### 3.4.1 General Considerations

The statistical analysis referring to primary and secondary objectives will be performed under the responsibility of the Sponsor's Biostatistics platform using SAS® Version 9.4 or later.

The statistical analysis will be conducted as follows:

- The database will be locked, and the study will be unblinded after all immunogenicity and safety data are collected for the follow-up period of 3 weeks after D22 (i.e., 21 days after the last vaccination).
- The final database lock will occur after the 12-month follow-up.

No adjustment for multiplicity regarding multiple comparisons between study doses is planned in this study.

For descriptive purposes, the following statistics will be presented:

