##### 4.2.4.3 Duration of the Study

The duration of the study is computed in days as follows:

- Maximum (Visit dates, Termination and safety follow-up date) – minimum (V01 date) + 1

The duration of the active phase of the study is computed in days as follows:

- Maximum (latest date of V02 or V03, date of termination during the active/intervention phase) – minimum (V01 date) + 1,

The duration of the D387 safety follow-up phase of the study is computed in days as follows:

- Maximum (date of D387 safety follow-up) – minimum (V02 or V03 dates, termination dates during the active/intervention phase) + 1

Note: Some participants will be vaccinated only with 1 dose and may decide not drop-out of the study.

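### The dose-selecting safety analysis stops 21 days after the last vaccination, does not bring in later SAEs and AESIs already reported by the lock, and has no clear cut for one-dose participants

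*SAP*

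**What the plan says.** SAP 3.5 and protocol 9.5 use the same sentence for the main analysis: immunogenicity "data and safety will include all data up to 21 days after the last vaccination". Both tie it to the choice of formulation; in protocol 9.5, "The results of this analysis will help in selecting the dose formulation for further clinical development". SAP 3.5 adds that the chosen formulation should be suitable on safety as well as on immune response. The 6- and 12-month data go to a final report after a second lock.

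The end of the cut is described in three ways:
- SAP 3.5 and protocol 9.5 count 21 days from the last vaccination.
- SAP 3.4.1 has the data "collected for the follow-up period of 3 weeks after D22 (i.e., 21 days after the last vaccination", which treats the two descriptions as the same. Protocol 9.4.1 does likewise.
- Protocol 10.1.5 gives the internal safety committee a blinded review "up to the D43 data unblinding for the main analysis".

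The events at issue are collected for much longer. Protocol 8.3.1 follows SAEs to 12 months after the last vaccination and AESIs throughout, and it says that "MAAEs will be collected throughout the study". Protocol 8.3.6 captures AESIs as SAEs. SAP 4.2.2.2.6 and 4.2.2.2.7 define SAE and AESI windows out to 387 days but assign them to neither lock.

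The SAP expects incomplete vaccination. SAP 4.2.4.3 notes: "Some participants will be vaccinated only with 1 dose and may decide not drop-out of the study". Protocol 7.1 and 8.3.2 keep these participants in safety follow-up.

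**The concern.** Enrolment is staggered, and the lock waits for the last participant's Visit 3 and for data cleaning. Participants enrolled early will by then be well past their own cut, and the sponsor will already have received any SAE or AESI reported for them. If the main tables follow SAP 3.5 as written, those events need not appear beside the immunogenicity results when the formulation is chosen. The next planned report follows D387, which is 344 days after D43 (387 − 43).

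One-dose participants raise a related question. They include people whose second dose was withheld for a significant allergic reaction or a vaccine-related SAE (protocol 7.1.2), so their serious events deserve a clear rule. The plan leaves two possible cuts for them, three weeks apart.

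**Working it through.** **Reproducing the study days.** From the schedule of activities:
- Dose 2: D01 + 21 = D22.
- Visit 3, "21 days post V02 (D43"): D22 + 21 = D43.
- Visit 4: D22 + 180 = D202.
- Visit 5: D22 + 365 = D387.

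All four agree with the documents. For a two-dose participant on schedule, the cut covers 42 of the 386 days from D01 to D387, or 10.9%.

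**The cut under each reading.**

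| Participant | Counted from own last dose (SAP 3.5) | Three weeks after D22 (SAP 3.4.1) |
|---|---|---|
| Doses on D01 and D22 | D43 | D43 |
| Doses on D01 and D29 (end of the +7 window) | D50 | D43 |
| Dose on D01 only | D22 | D43 |

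The readings agree only for the on-schedule participant. Solicited reactions are collected for 7 days after each dose and non-serious unsolicited AEs for 21 days (protocol 8.3.1), so for one-dose participants the ambiguity mainly concerns SAEs, AESIs and MAAEs. Protocol 9.4.3 lists MAAE summaries within 21 days of each vaccination and then "from D01 to D42, from D43 to D202, from D203 to D387, and overall study". For a one-dose participant the 21-day window ends at D22, while the D01 to D42 window does not.

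**Follow-up past the cut at the lock (assumed inputs).** Let enrolment be uniform over A days and the lock fall L days after the last Visit 3. Neither A nor L is in the documents. Mean follow-up past the cut for two-dose participants is A/2 + L, and its share of follow-up accrued by the lock is (A/2 + L) / (A/2 + L + 42).
- A = 30, L = 30: 15 + 30 = 45 days; 45/87 = 52%.
- A = 120, L = 90: 60 + 90 = 150 days; 150/192 = 78%.
- A = 180, L = 90: 90 + 90 = 180 days; 180/222 = 81%.

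These are elapsed days, not days with a safety interview. No visit falls between D43 and D202, a gap of 159 days. The share of participants who reach Visit 4 by the lock is (A + L − 159)/A when that lies between 0 and 1. It is 0% for A = 30, L = 30, because the longest time past D43 is only 60 days. It is (210 − 159)/120 = 43% for A = 120, L = 90.

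**One-dose participants (assumed share).** If 2%, 5% or 10% of 700 (14, 35 or 70 people) were cut at D22 instead of D43, 21 days each would be lost: 294, 735 or 1,470 person-days. Against 700 × 42 = 29,400 person-days, that is 1%, 2.5% or 5%.

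**The case against.** The strongest reply is that the plan is silent on later events and does not exclude them. Saying what an analysis will include does not forbid a listing of later SAEs, and SAP 4.2.2.2.6 and 4.2.2.2.7 already define longer windows. The sponsor receives SAEs within 24 hours, is unblinded at participant level at the lock, may take unblinded early looks at safety, and has a safety team with its own SAP. The main analysis is one input to the choice of formulation. A study-day cut also gives equal, cleaned follow-up, which is defensible in a descriptive study.

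Much of this stands. A reader might infer that the formulation would be chosen in ignorance of later serious events; the documents do not support that. What the reply does not supply is a planned comparison by group. The early looks are optional, with no stated content or timing, and protocol 10.1.5 says that there will be no early safety data review. The committee's assigned review is blinded up to the D43 unblinding. The safety team's separate SAP has no stated link to choosing the formulation.

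A reader might also infer that one-dose participants are definitely cut at D22, or that they are followed for less time. The first is only one reading, since SAP 3.4.1 and protocol 9.4.1 point to D43. The second is wrong: protocol 7.1 keeps them in safety follow-up, and 8.3.2 requires the 12-month contact for anyone with at least one dose. Only an interim table could be shorter.

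**Conclusion.** The point holds in limited form. SAP 3.5 and protocol 9.5 set a 21-day safety cut for the analysis that informs the choice of formulation and do not bring in SAEs and AESIs that are reported by the lock but began later. The cut for one-dose participants is undefined between D22 and D43.

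The number of events affected cannot be derived from the documents. The 52% to 81% range rests entirely on assumed enrolment and lock times and counts elapsed days, much of it before any scheduled contact after D43. It shows that the follow-up involved could be substantial; it does not measure missing data. The one-dose effect is small in person-days, at 1% to 5% for assumed shares of 2% to 10%, but it can fall on people whose vaccination stopped for a related event.

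The SAP has no MAAE endpoint or analysis at all. That is a separate gap between protocol and SAP and not a result of this cut.

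**What to change.** In SAP 3.5 and protocol 9.5:
1. Keep the 21-day safety tables and the D43 immunogenicity analysis unchanged.
2. State that the safety cut for one-dose participants is D43, matching Visit 3 timing. Say explicitly how the cut applies when the second dose is given late in its window.
3. Add to the main analysis a table or listing by group of all SAEs and AESIs with onset up to a fixed calendar cut-off before the lock, in all vaccinated participants including those with one dose. Split it into onset within 21 days of a vaccination and later, and give follow-up time per group.
4. If MAAEs are shown, list them as reported, with a note that no visit falls between D43 and D202, so capture in that interval is incomplete.

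The cost is a few sentences and one additional output. Events after D43 will be less fully cleaned, and follow-up length will vary between participants, although randomisation should balance it across groups. The calendar cut-off should be fixed before unblinding.
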